7.3.7 Identification of participant subgroups and heterogeneity of treatment effects

The goal of analyses to assess the heterogeneity of treatment effects is to understand whether comparative effectiveness between the care coordination models varies by subgroup. There is sufficient evidence to hypothesize that the social/medical model may be more effective for patients with high social needs or low socioeconomic status.^{58,59} We will also assess heterogeneity of treatment effects by age, sex, race/ethnicity, and disease status subgroups, but without an a priori hypothesis about the potential differences. Heterogeneity of treatment effects will be appropriately assessed using interaction terms in the statistical models described above.⁶⁰

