7.1 Outcomes

Our outcomes fall into three categories: care quality (drawing on statewide quality measures reported by MNCM), utilization (drawing on insurance claims data collected by payor partners), and patient-centered/patient-reported outcomes (collected directly from care coordination patients who agree to complete a survey). Section 5 describes how data will be collected. **Table 3** summarizes study outcomes. Timing of outcome assessment will be anchored by the first date of receiving care coordination services, thereby creating a consistency across comparators and mitigating potential sources of bias due to timing. Modifications to these definitions and planned analysis may arise if certain data quality and availability thresholds are not met.

Table 3: Study Outcomes

Outcome measure	Definition	Source	Primary/ Secondary	Follow-up duration

Care Quality from the healthcare professional perspective				
Overall care quality	Composite measure of overall quality comprised of the percentage of all care quality outcomes in which a patient qualifies and meets quality criteria for	MNCM quality measures	Primary	12m
Asthma care at goal*	Asthma pts. with asthma control test (ACT) score >19	MNCM quality measures	Secondary	12m
Breast Cancer Screening* (up-to-date)	Women 50-74 yrs old who received a mammogram in the past one year	Health plan claims	Secondary	12m
Chlamydia Screening* (up-to-date)	Female patients 16-24 yrs old who had a screening test for chlamydia	Health plan claims	Secondary	12m
Colorectal Cancer Screening* (up-to-date)	50-75 yr old pts. up-to-date for an approved screening test	MNCM quality measures	Secondary	12m
Depression improvement*	PHQ-9 score <5 for test nearest to end of follow-up period	MNCM quality measures	Secondary	12m
Diabetes care at goal (including component measures)	All-in-one measure of control A1c, blood pressure, statin use, & smoking	MNCM quality measures	Secondary	12m
Vascular care at goal (including component measures)	All-in-one measure of control of blood pressure, statin use, & smoking + aspirin use in patients with vascular disease	MNCM quality measures	Secondary	12m
A1c control*	Hemoglobin A1c ≤ 7% in patients with diabetes	MNCM quality measures, clinic data	Secondary	12m
A1c level	Hemoglobin A1c in patients with diabetes	MNCM quality measures, clinic data	Secondary	12m

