Rating of care coordinator	CG-CAHPS (adapted)	Patient survey	Secondary	6m-18m
Shared decision making	3-item CollaboRATE ⁴⁴	Patient survey	Secondary	6m-18m
Perceived care integration	4-item IntegRATE ⁴⁵	Patient survey	Secondary	6m-18m
Going without care due to cost	National Health Interview Survey	Patient survey	Secondary	6m-18m
Out-of-pocket medical costs	Medical Expenditure Panel Survey	Patient survey	Secondary	6m-18m
Medication and care burden	Modified subset of 7-item Treatment Burden Questionnaire (TBQ) ⁵⁰	Patient survey	Secondary	6m-18m
Social needs	Modified subset of 10-item CMS HRSN Screening Tool ⁵¹	Patient survey	Secondary	6m-18m
Insurance coverage	State Health Access Data Assistance Center (SHADAC) Coordinated State Coverage Survey	Patient survey	Secondary	6m-18m

* Subcomponent of overall care quality composite outcome

Notes: MNCM = MN Community Measurement; m = months.

[figure not shown]

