outcomes, we will also evaluate a composite outcome representing the proportion of applicable care quality outcomes that are met by a given patient. We intend to primarily evaluate this proportion as a continuous variable in a linear or tobit regression model that follows the structure in equation (1) above with the inclusion of a patient's baseline composite outcome as a covariate. However, based on the empirical distribution, we may also evaluate transformations to binary or multilevel categorical versions of this outcome as warranted.

Utilization outcomes for Aim 1 analyses will be evaluated both as binomial (any occurrence vs. none) and as counts. GLMMs will follow the framework of equation (1) above, however, for the underlying distribution of count outcomes we will assume a Poisson (or negative binomial, as appropriate) distribution with a log (as opposed to logit) link function. We anticipate a similar modeling approach for quantitative analyses of the impact of care coordination type on patient-reported outcomes (again adapting assumptions of the underlying distribution and corresponding link function, specific to the nature of each outcome variable). The main exception will be that we will not have baseline values for patient-reported measures, given that they will only be collected at a single time point in follow-up. Reporting of medical costs as a secondary outcome will follow PCORI standards.⁵³

Primary results for Aim 1 analyses will be reported as odds ratios, rate ratios, or (beta) differences (comparing the medical/social care coordination model to the nursing/medical model), with 95% confidence intervals, for each study outcome.

All Aim 1 analyses as described above will be replicated for both the Primary and Historical cohorts, and reported separately. To evaluate whether cohort-specific estimates statistically differ with respect to a given outcome, we will estimate pooled (Primary + Historical) models and evaluate the significance of the Wald test for the interaction term (*Cohort*CC Type*). Additionally, for the Historical cohort, care quality and utilization outcomes may potentially be available for up to 3 years from the onset of care coordination. Where data is available, we will estimate the impact of care coordination type on 1-year, 2-year, and 3-year outcomes respectively, using the framework described above, within the Historical cohort.

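### Section 7.3.7: age, sex and disease-status interactions on the primary quality composite can reflect measure mix if the care model's effect differs between measures

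*Combined protocol and SAP*

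**What the plan says.** Table 3 (section 7.1) defines the primary quality outcome: "Composite measure of overall quality comprised of the percentage of all care quality outcomes in which a patient qualifies and meets quality criteria for". Section 7.3.1 describes it as a "composite outcome representing the proportion of applicable care quality outcomes that are met by a given patient". The rows of Table 3 with an asterisk are its components ("Subcomponent of overall care quality composite outcome"). Who counts for each component depends on the following:

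- **Sex and age:** mammography ("Women 50-74 yrs old who received a mammogram in the past one year") and chlamydia ("Female patients 16-24 yrs old who had a screening test for chlamydia").
- **Age:** colorectal screening ("50-75 yr old pts. up-to-date for an approved screening test"). Appendix B also limits asthma to patients under 51.
- **Disease:** A1c ("Hemoglobin A1c ≤ 7% in patients with diabetes"); aspirin and statin use (vascular disease); tobacco use (diabetes or vascular disease); asthma and depression (by diagnosis).
- **Blood pressure control:** Table 3 gives a threshold and no disease restriction.

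Section 7.3.1 models the composite by linear or tobit regression, with a random clinic intercept and the baseline composite as a covariate. It also fits a separate binary model to each measure. Section 7.3.7 then says: "We will also assess heterogeneity of treatment effects by age, sex, race/ethnicity, and disease status subgroups". It has no prior hypothesis for these factors and tests them by interaction terms in the models already described. No passage adds a term for measure mix, or says how a composite interaction is to be read against the single measures.

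**The concern.** The subgroup factors also set the denominator of the outcome. Two subgroups can therefore have composites made of different measures. Suppose one care model improves screening and nothing else, by the same amount in every eligible patient. The composite then rises most where screening is a large share of the applicable measures, and the interaction term picks this up. Subgroup main effects and the baseline composite do not remove it.

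Section 7.3.7 aims to learn whether comparative effectiveness varies by subgroup. An interaction that comes from mix could be reported as the model working better in older patients, or in patients without diabetes. Section 13.6 expects the results to guide which model is promoted. Section 7.3.4 may pool the cohorts to gain power for subgroup analyses, and that would also make such an artefact easier to detect.

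**Working it through.** **1. The plan's own figure.** Section 7.2.1 states that a 1-point composite difference is detectable in all scenarios (two-sided 5%, 80% power, ICC 0.01, 55:45 split). It gives no SD, so only the implied SD can be found. Detectable difference = 2.8016 × SD × √[(1/0.55 + 1/0.45) × (1 + (m − 1) × 0.01) / N].

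- 298 clinics × 10 patients: 2.8016 × √(4.0404 × 1.09 / 2,980) = 0.1077, so SD ≤ 1/0.1077 = 9.3.
- 397 clinics × 50 patients: 2.8016 × √(4.0404 × 1.49 / 19,850) = 0.0488, so SD ≤ 20.5.

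The plan gives no power for any interaction. The 1-point target serves below only as a yardstick.

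**2. Algebra.** Let a patient qualify for n measures, and let d_m be the care-model effect on measure m, the same for every eligible patient. The effect on that patient's composite is (1/n) Σ d_m over the n measures. If all d_m equal d, this is d for everyone and there is no interaction. If the d_m differ, it depends on which measures apply.

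**3. Hand counts.** These use Table 3 eligibility, blood pressure limited to diabetes or vascular disease, and no vascular disease, asthma or depression. Cells are composite gains in points.

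| Patient | Measures (screening) | +5 on screening only | +5 on other measures only | +5 on all |
|---|---|---|---|---|
| Woman 60, no listed disease | 2 (2) | 10/2 = 5.0 | 0 | 5.0 |
| Woman 60, diabetes | 5 (2) | 10/5 = 2.0 | 15/5 = 3.0 | 5.0 |
| Man 60, diabetes | 4 (1) | 5/4 = 1.25 | 15/4 = 3.75 | 5.0 |
| Woman 40, diabetes | 3 (0) | 0 | 15/3 = 5.0 | 5.0 |

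If blood pressure applies to everyone, the woman in the first row has three measures and gains 10/3 = 3.3 from screening. Her gap to the woman of 60 with diabetes falls from 3.0 to 1.3 points. The age gap between the two women with diabetes (2.0 against 0) does not change.

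**4. Simulation.** From the documents: 397 clinics × 57 patients and 45% medical/social (section 7.2.1), and 62% women (section 13.7.1). Assumed: age mean 60, SD 17; diabetes 35%, vascular disease 20%, depression 35%, asthma 15%; and the measure rates. The model is linear with a random clinic intercept, the baseline composite, main effects and the interaction. Blood pressure is restricted to diabetes or vascular disease. There are 300 cohorts per scenario, and no measure's effect differs by subgroup. Cells are the percentage significant at 5%.

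| Effect | Sex | Age ≥50 | Diabetes |
|---|---|---|---|
| None | 7 | 4 | 2 |
| +3 points on every measure | 4–6 | 4–5 | 3–4 |
| Odds ratio 1.2 on every measure | 6 | 5 | 3 |
| +3 on non-screening measures only | 5 | 28 | 21 |
| +5 on non-screening measures only | 7–11 | 59–64 | 43–46 |
| +5 on screening only | 7 | 64 | 43 |

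The Monte Carlo SE near 5% is √(0.05 × 0.95 / 300) = 1.3 points. In the +5 non-screening scenario the mean apparent interactions were −0.4 (sex), −2.5 (age) and +1.8 points (diabetes).

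**5. Variants, with effects of +3 and +5 on screening only.**

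- No baseline composite, asthma 12%, age group 50–75, 200 cohorts: age 41% and 76%; diabetes 19% and 35%.
- Baseline composite included, 200 cohorts: diabetes 22–58% with blood pressure restricted. With blood pressure for everyone, diabetes 6–7% and age 36–86%.
- Baseline composite included, 60 cohorts: age 32% and about 80%; sex about 3–8%; diabetes 27–48% with blood pressure restricted and 7–13% with it for everyone.

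A +5 effect on depression only gave 37% (age) and 29% (diabetes) in the first variant. With blood pressure for everyone, both were 6% in the second.

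**6. Measure-level model.** This has one row per patient per applicable measure, with measure-by-care-model terms. In the +5 non-screening scenario its mean subgroup-by-care-model term was about 0. It was significant in 5–6% (sex), 4–5% (age) and 7% (diabetes) of cohorts. The first variant gave 3–7%. The 60-cohort variant gave 5–12%, with a Monte Carlo SE near 5% of √(0.05 × 0.95 / 60) = 2.8 points.

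**The case against.** A reader might infer that these tests always report measure mix as differing effectiveness, or that they cannot answer the question in section 7.3.7. The documents do not support that. Mix alone shifts the subgroup main effect, not the interaction, and the documents do not say that effects differ between measures. With no effect or an equal effect, rejection stays near 5%. Nor is sex a material case: it stays between 3% and 11% throughout.

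Other objections carry weight:

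- **Single-measure models.** Section 7.3.7 also applies to the binary model for each measure, and those interactions are free of mix. This stands as a partial safeguard. But these outcomes are secondary and are fitted within baseline-status groups, and nothing ties them to the reading of the composite.
- **Estimand.** If a care model raises screening, older patients' composites do rise more. On the outcome as defined, that difference is real. The fault lies in reading it as a different response by patient type.
- **Inputs.** The disease-status result turns on who counts for blood pressure control. Appendix B starts colorectal screening at 45, where Table 3 says 50; that moves the age boundary but does not remove it. Mammography comes from claims, which cover about 45% of patients. If it drops out for the rest, the woman of 60 with diabetes has four measures and gains 5/4 = 1.25 instead of 2.0.
- **Status.** These subgroup tests have no prior hypothesis. The hypothesised ones (social needs, socioeconomic status) do not set eligibility for any measure.

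**Conclusion.** The point holds conditionally. Age, sex and disease status both define the subgroups and select the measures in the composite, and the plan has no safeguard for reading that interaction. It misleads only if the care model's effect differs between measures. That is plausible when the comparison is the addition of a social worker, but the documents do not establish it.

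With 3 to 5 points on screening only, the age interaction is significant in about 30% to 80% of simulated cohorts (32% to 86% across runs). Diabetes gives about 20% to 50% with blood pressure restricted (19% to 58% across runs) and about 6% to 13% without restriction. Sex is affected little. All rates rest on assumed prevalences, measure rates and effects. The overall Aim 1 comparison is not in question. This is a worthwhile, cheap improvement, mainly for age.

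**What to change.** Keep the patient-level composite interaction and add two statements to section 7.3.7:

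1. For age, sex and disease status, the composite interaction is reported with a companion measure-level model. That model has one row per patient per applicable measure, measure and subgroup main effects, measure-by-care-model terms, the subgroup-by-care-model term, and allowance for clustering by clinic and patient.
2. The composite interaction is read as differing effectiveness only if the within-measure subgroup-by-care-model term supports it.

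The cost is SAP wording and a modest amount of modelling on person-level quality and claims data that MNCM already supplies (sections 5.1.2 and 5.1.3). There are two drawbacks. Patients with more measures get more weight in the companion model, so it should not replace the composite. Disease-status terms rest only on measures that both subgroups share.

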7.3.8 Bias Mitigation

To mitigate bias, we will: 1) rely on subject area experts on our project team and in the clinics to identify anticipated confounders for the relationship(s) between coordinated care model and study outcomes; 2) use directed acyclic graph methods to diagnose potential sources of confounding or selection bias, and identify analytic approaches to correct such biases⁶¹; 3) evaluate imbalances in empirical distributions of covariates with respect to care coordination model, and their associations with study outcomes (requisite criteria for presence of confounding); 4) employ appropriate analytic strategies (stratification, multivariable modeling, inverse probability weighting)⁶²; 5) conduct sensitivity or quantitative bias analyses to calculate reasonable bounds for study estimates under varying assumptions⁵⁷; and 6) acknowledge remaining limitations to be considered when interpreting our study results.

8 Qualitative Analysis Plan

Drs. [name], [name], and [name] in consultation with [name] will lead the qualitative data analysis of participant interviews. Qualitative data analysis will be approached from two perspectives: at baseline for survey development (Phase 1) and again in the final year (Phase 2) to understand meaning, implications, and recommendations regarding the study findings from the perspectives of patients, care coordinators, and clinicians/leaders.

In Phase 1 patient, clinician/leader, and care coordinator interviews, we will first conduct a rapid analysis of any content that needs to be incorporated in the subsequent surveys of being developed for patients or care coordinators, which will be followed by a more deliberative directed content analysis approach. Following interview completion, audio recordings will be transcribed using a professional transcription service. These transcripts will be discussed by the analysis team as they are completed in order to identify immediately actionable information regarding survey development. Then, interview

data (transcripts and field notes) will be analyzed using an inductive, descriptive approach to assess, code, and categorize the data into *a priori* constructs and empirical constructs arising from the interview data. *A priori* constructs will be derived from prior work and the literature that is relevant to the survey development focus for each participant group. Constructs will be mapped onto developing measurement frameworks that will form the foundation of survey development for each study population. Coding differences will be discussed until consensus is reached on a final coding structure that will then be applied to all data. The survey development team will use the findings of the data analysis to guide survey development for patient and care coordinator surveys.

The data analysis for Phase 2 patient and care coordinator interviews will utilize a strategic and thematic approach to explore clinician/leader, care coordinator, and patient perceptions of study results and their implications.⁶³ A thematic analysis will be applied that is flexible and accessible in interpretation and application.⁶⁴ Data will be systematically coded into categories, themes, and patterns emerging from and grounded in the data with an *a priori* focus on identifying the processes and elements of care coordination as experienced by clinicians and leaders, and the perception of study results and their applications from a variety of study participants. Open coding will be used to create the initial coding frame; data will then be coded into categories with similar characteristics.⁶⁵ Classification schemes and typologies will be used to identify and develop emerging themes, concepts, and patterns arising from and grounded in the data.

NVivo, a qualitative data-analysis software program, will be used for the data analysis. Issues of trustworthiness and rigor in the analysis defined as credibility, transferability, dependability, and confirmability of the data (a qualitative equivalent to validity and reliability) will be addressed through a number of strategies.⁶⁶⁻⁶⁸ Confirmability and dependability will be addressed by maintaining a data codebook and audit trail mapping decision points in the analysis. Negative case analysis will be conducted on individual interviews that do not fit evolving patterns in the data. Credibility will be addressed by having the analysis team agree on final themes and patterns in the data. Issues of transferability will be addressed through triangulation with other data sources. This is particularly important in Phase 1 as the data will be used in triangulation with other sources to inform and guide survey development. In Phase 2 interview data will be compared and triangulated with other study data to clarify and enhance quantitative findings.

9 Data Quality Assurance

9.1 Missing Data

9.1.1 Methods to prevent and monitor missing data

The absence of documentation of a care process or vital sign in the care quality database should not be interpreted as a missing value, but rather as indicative of a care process or test not having been performed. Likewise, absence of utilization indicated by billing claims almost always indicates that the utilization (such as a hospitalization) did not occur. Truly missing observations (e.g., SBP measured, value not available) will be extremely rare, undetectable, and assumed to be missing at random (perhaps conditional on available measures). For surveys, CESR will employ state-of-the-art methods to minimize unit and item nonresponse for patient-reported outcomes. For item non-response, we expect <5% missing data on any single item.

9.1.2 Statistical methods to handle missing data and statistical uncertainty due to missing data

By definition, exposure status for Aim 1 analyses (care coordination type) will not be missing; this classification is determined at the level of participating clinics. Patients that are missing outcome measures will be excluded from analyses specific to that outcome. For primary analyses that include parameters derived by interview/survey, non-responders will be excluded. In sensitivity analyses, we will evaluate differences in available measures by survey response status, and construct weighted (by likelihood of response) models to reconstruct the full population and supplement results from complete case analyses. Where non-survey covariate values are substantially missing (e.g., >20%), these covariates will not be included in primary models. Where non-survey covariate values are missing for <20% of a given analysis population, we will use a complete case approach for primary analyses. In sensitivity analyses, we will use multiple imputation (using the R package ‘MICE’) to fill in non-survey covariate values that are missing for <20% of a given analysis population, and reconstruct models of interest with partially imputed input data. Lastly, we will conduct bias analyses to quantify the potential impact of covariate missingness on outcome-specific model results as needed.^{69,70}

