9.1.3 Monitoring reasons for dropout and missing data

Utilization data may be incomplete if a patient switched insurance plans during the pre or post index period (note that switching among Medicaid or state-sponsored plans will generally not be lost to follow-up within the MN DHS data systems). The disposition of each contact attempt to complete a survey will be documented by the survey administrator(s). For mailings, this includes undeliverable addresses and active refusals. For telephone surveys, these dispositions include noncontact, refusal, ineligibility, and bad telephone number.

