17.3 Appendix C: Claims data specifications

These data specifications are for collection of Utilization Outcomes data as described in Section 5.1.3

General Rules for Administrative Claim files:

- Date Range: One-year pre and post enrollment in Health Care Homes
- Time period is based on discharge date when applicable
- Payers should submit paid claims and final claims only (exclude denied claims)
- Partial facility claims are acceptable if the full claim is not available
- Notes: Medicare Cost Plan patients will not have hospital claims available
- Note: Pharmacy claims are not always available for commercial patients
- TBD: multiple payers for same patient
- Note: dollar amounts are for RVU study, not for a cost comparison

Summary of changes (March 2023):

- Added product type code 77 for Minnesota Senior Care Plus (MSC+); see page 2, Enrollment Data File, Element Order I

Enrollment Data File

Submit one record per patient per enrollment period. Patients may be listed in multiple rows if the enrollment was not continuous.

Element Order	Who is responsible for supplying data?	Field Name	Details	Required or Situational	Format/Field Length	Error Causes
A	MNCARES	Current Primary Insurance Member ID	
• Unique patient identifier for health plan• Do NOT use SSN.	R	String; up to 50 characters	Blank fields
B	MNCARES	Study ID	
• Unique MNCARES assigned non-PHI study ID for patient.	R	String; up to 10 characters	Blank fields
C	MNCARES	Patient Master Index	
• From Clinic Data File	S		

Element Order	Who is responsible for supplying data?	Field Name	Details	Required or Situational	Format/Field Length	Error Causes
D	MNCARES	Medical Record Number	
 • Unique patient identifier for clinic EMR • Do NOT use SSN. 	R	String; up to 50 characters	Blank fields
E	MNCARES	Patient First Name	Enter the first name of the patient.	R	String	Blank fields Values outside allowable range
F	MNCARES	Patient Middle Name	Enter the middle name of the patient if available.	S	String	
G	MNCARES	Patient Last Name	Enter the last name of the patient.	R	String	Blank fields Values outside allowable range
H	MNCARES	Patient Date of Birth (DOB)		R	mm/dd/yyyy or m/d/yyyy	Blank fields

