I	Health Plan	Product Type	
 • 1 = Commercial • 5A = Medicare Advantage • 5C = Medicare Cost • 6 = MSHO • 7A = Medicaid (MNCare) • 7B = Medicaid (PMAP) • 7C = Medicaid (Hennepin Health) • 8 = SNBC (Special Needs Basic Care) • 77 = Minnesota Senior Care Plus (MSC+) 	R	String; 2 digits	Blank fields
J	Health Plan	Insurance Plan Enrollment Start Date		R	mm/dd/yyyy or m/d/yyyy	Blank fields
K	Health Plan	Insurance Plan Enrollment End Date		R	mm/dd/yyyy or m/d/yyyy	Blank fields
L	Health Plan	Pharmacy Data availability	
 • 0=No • 1=Yes • Is pharmacy data available in the plan data warehouse? 	R	String; 1 digit	Blank fields

Professional Data File (HCFA 1500)

Standard claim form for physicians and other health care professionals.

Submit one line per patient per procedure claim. Patients may be listed in multiple rows for multiple procedure claims.

Element Order	Field Name	Details	Required or Situational	Format/Field Length	Error Causes
A	Study ID	Unique MNCARES assigned non-PHI study ID for patient	R	String; up to 10 characters	Blank fields
B	Claim ID		R		Blank fields
C	Provider First Name	Enter the first name of the provider.	S	String	
D	Provider Middle Name	Enter the middle name of the provider if it is recorded in the medical record.	S	String	
E	Provider Last Name or Facility Name	Enter the last name of the provider.	R	String	Blank fields Values outside allowable range
F	Provider Specialty Type	Enter the code that corresponds to the Provider's Specialty. Please refer to the Standard Medicare Taxonomy Codes .	R	String; up to 15 characters	Blank fields Values outside allowable range
G	Clinic Site of Service		R	Number; up to 2 digits	Blank fields Values outside allowable range
H	Start Date of service		R	mm/dd/yyyy or m/d/yyyy	Blank fields
I	End Date of service		R	mm/dd/yyyy or m/d/yyyy	Blank fields
J	Procedure Code	Enter the CPT/HCPCS code that corresponds to the procedure claim. Do not include modifiers.	R	String; 5 characters	Blank fields
K	Modifier(s)		S	String; 8 characters	
L	Units		R		Blank fields
M	Billed Charges	To be used only for calculation of Relative Value	R	Number, 2 digits	

Facility Data File (UB04)

Hospital and Facility Header File, one line per admission or bundle of outpatient services.

Element Order	Field Name	Details	Required or Situational	Format/Field Length	Error Causes

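### Section 9.1.1 reads an absent claim as almost always no event, but Appendix C accepts members and enrollment gaps for which claims cannot be seen, and no section says when a claims outcome is missing

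*Combined protocol and SAP*

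**What the plan says.** Section 9.1.1, on preventing and monitoring missing data, says that "absence of utilization indicated by billing claims almost always indicates that the utilization (such as a hospitalization) did not occur". It adds that genuinely missing values will be very uncommon and cannot be detected.

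Appendix C describes the claims that payors will send. Its general rules note that "Medicare Cost Plan patients will not have hospital claims available" and leave one item open: "TBD: multiple payers for same patient". The Enrollment Data File lists "5C = Medicare Cost" among the accepted product types and says that "Patients may be listed in multiple rows if the enrollment was not continuous". Product type and plan enrollment start and end dates are all required fields.

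Section 9.1.3 concedes that "Utilization data may be incomplete if a patient switched insurance plans during the pre or post index period", with the qualification that moves among Medicaid or state plans are generally not lost. It gives no analytic consequence. Section 9.1.2 says that "Patients that are missing outcome measures will be excluded from analyses specific to that outcome", without saying when a claims outcome is missing.

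For utilization outcomes, Sections 4.2.2 and 7.3.6.2 require coverage by a participating payor, with no minimum enrolled period and no restriction by product. Section 2.3 describes utilization as rates, and Section 7.3.1 plans Poisson or negative binomial models reported as rate ratios. Neither names a person-time denominator or an offset. The follow-up-duration covariate in Section 7.3.6.4 applies to survey outcomes only.

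**The concern.** Hospitalizations and emergency department (ED) visits are primary outcomes (Section 7.1, Table 3). The event that Section 9.1.1 uses as its example is the one that Medicare Cost members' data cannot show. If an absent claim is taken as zero, such a member has zero hospitalizations whatever happened, and a month outside plan enrollment counts as event-free. Both kinds of gap can be identified from required fields, so they are not undetectable.

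What is at stake is first the level of each rate. The Medicare Cost gap lowers hospitalizations, readmissions and cost; enrollment gaps lower every claims outcome. The 12-month pre-period values carry the same error. The contrast between medical/social and nursing/medical clinics is affected only under a further condition, taken up below.

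**Working it through.** **1. The passages side by side.** For a Medicare Cost member, Section 9.1.1 points to zero hospitalizations. Appendix C says the claims are unavailable, which points to missing. Section 9.1.2 would act on missing, but nothing connects a product type or an unenrolled period to that status. The plan therefore supports two codings of the same patient and does not choose between them.

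**2. The plan's own figures.** Section 7.2.1: 57 × 0.45 = 25.65, or 26 claims patients per clinic, as stated. Section 7.2.2: 66 × 0.45 = 29.7, or 30, as stated. The 10% detectable difference in hospitalizations cannot be reproduced, because the text gives no event rate or dispersion. As a plausibility check, assume a rate λ of 0.5 to 1.0 per year, dispersion k of 0 to 2, and 75% to 100% of 397 clinics split 55/45:

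MDE = exp{2.80 × √[(1/λ + k) × (DE/m) × (1/J₁ + 1/J₂)]} − 1, with m = 26 and DE = 1 + 25 × 0.01 = 1.25.

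This gives about 6% to 15% (λ = 0.5, k = 1, all clinics: 11.3%), so 10% is plausible but not verifiable.

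**3. Effect on levels.** The documents give no Medicare Cost share, so c is an assumption. At average risk, the observed rate is the true rate × (1 − c). For c = 5%, 10% or 15%, the rate is understated by 5%, 10% or 15%.

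**4. Effect on the contrast.** With no true difference, the crude rate ratio (medical/social over nursing/medical) is (1 − c₁)/(1 − c₀):

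| c₁ / c₀ (assumed) | Crude rate ratio |
|---|---|
| equal shares | 1.00 |
| 5% / 7% | 0.95/0.93 = 1.022 |
| 5% / 10% | 0.95/0.90 = 1.056 |
| 5% / 15% | 0.95/0.85 = 1.118 |
| 10% / 5% | 0.90/0.95 = 0.947 |

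Section 7.3.1 implies adjustment for baseline utilization. Medicare Cost members would also show zero at baseline, so this removes part of the distortion. With gamma-Poisson counts (rates 0.3, 0.5 or 0.8 per year; gamma variance 0.5, 1 or 2) and several codings of the baseline count, the adjusted ratio is about 1.02 to 1.05 for 5%/10%, 1.04 to 1.10 for 5%/15%, and 1.00 for equal shares. A separate covariate level for Medicare Cost also returns 1.00.

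For the any-versus-none outcome, let p be the true chance of any admission. The crude odds ratio is [(1 − c₁)p/(1 − (1 − c₁)p)] ÷ [(1 − c₀)p/(1 − (1 − c₀)p)]. Over the same grid p runs from 1 − 1.6^(−0.5) = 0.209 to 1 − 1.4^(−2) = 0.490. For 5%/15% this gives 1.15 to 1.22 crude, and 1.11 to 1.17 after adjusting for any baseline admission.

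**5. Enrollment gaps without an offset.** With mean observed months assumed in each model, the crude factor is 11.5/11.5 = 1.00, 11.2/11.5 = 0.974 or 10.8/11.5 = 0.939.

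**6. ED visits.** Table 3 defines these by CPT codes, and procedure codes also come through the professional claims file. Whether the Medicare Cost gap reaches them cannot be settled from the documents. Enrollment gaps do reach them.

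**The case against.** The strongest reply is that Section 9.1.1 makes a general observation, hedged by *almost always*, and gives no coding instruction. Its remark about undetectable missing values takes a blood-pressure reading as its example. Section 9.1.2 could be read to exclude Medicare Cost members from the hospitalization analysis, and Section 9.1.3 itself calls data after a plan switch incomplete. Rates and rate ratios may imply a time denominator. Payors verify coverage (Sections 5.1.3 and 6.1) and return dated enrollment records. Section 6.4 promises data dictionaries, Section 10 schedules a preliminary assessment of each dataset, and Sections 7.1, 7.3.8 and 9.1.4 leave room for changes and bias analyses.

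Much of this stands. A reader might infer that the plan orders these patients to be coded as zero; it does not, although that is the most direct reading. A reader might also infer that coverage during the study windows is unknown, because Appendix A asks clinics for the insurance on file at the data pull. That field serves matching. Prior insurance is also requested where obtainable, and the payors' enrollment dates come later, so coverage can be established.

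What does not stand is that any of this supplies the rule. None of these sections says which product types or enrolled periods make a claims outcome observable. The sensitivity analyses specified in Section 9.1.2 deal with survey non-response and covariates, not with unobserved claims time.

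**Conclusion.** The concern holds as a gap in a prespecified rule for a primary outcome, and it should be fixed. Section 9.1.1 and Appendix C conflict, and Section 9.1.2 cannot resolve the conflict without a definition of a missing claims outcome. If absent claims are scored as zero, levels are understated in proportion to the Medicare Cost share (hospitalizations, readmissions, cost) and to unenrolled time (all claims outcomes). Every share, rate and coverage time used to size this is an assumption.

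A reader might go on to infer that the care-model comparison is biased. The documents do not support that. Bias needs the shares to differ by model and the covariates not to capture the difference. No such difference is reported, and insurance coverage is a candidate covariate (Table 2), though its coding is not given. The contrast figures show only that an imbalance of 5 to 10 percentage points could produce a distortion that is not negligible beside the 10% difference the study targets. Nor do the documents show that the Medicare Cost gap affects ED visits.

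**What to change.** (a) Reword Section 9.1.1 so that an absent claim counts as zero only while the patient is enrolled in a product that supplies that type of claim.

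(b) Treat hospitalizations, readmissions and cost as missing for Medicare Cost periods, so that the exclusion in Section 9.1.2 applies to patients with no other observed time.

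(c) Use the enrollment dates, with date of death where recorded, for a log(enrolled time) offset in the count models and for baseline rates.

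(d) Add a sensitivity analysis in continuously enrolled patients, including the any-versus-none outcomes. It belongs there rather than in the primary analysis because it selects on coverage after the index date.

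(e) Report the Medicare Cost share and mean enrolled months by care model and cohort.

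No new data are needed; the work is SAP wording and a few lines of code. There are three costs. Hospitalization results no longer cover Medicare Cost members. The offset assumes that events are proportional to enrolled time. And the hospitalization sample falls by an unknown share: at an assumed 5%, 10% or 15%, by about 516, 1,032 or 1,548 of 26 × 397 = 10,322 Primary Cohort patients, and by 494, 987 or 1,481 of 30 × 329 = 9,870 Historical Cohort patients.

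The detectable difference scales with √[(1 + (m − 1) × 0.01)/m]. Going from m = 26 to 24.7, 23.4 or 22.1 multiplies it by 1.021, 1.043 or 1.068, so it is about 2% to 7% larger than planned. Compared with keeping these patients as zeros, nothing is lost: in a simulation with 10% in Medicare Cost, the standard error of the log rate ratio was 0.0382 coded as zero and 0.0377 excluded.
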